Using a CBPR approach, we completed qualitative interviews with 20 AI men and women on the Apsalooke Reservation who had a CI diagnosis. After we developed a culturally consonant method for co-analyzing the data with our community advisory board (CAB), we analyzed the data and used the findings to develop a conceptual framework and intervention for understanding and improving CI management, something that had not existed for this population. Our intervention will be tested across multiple CIs, as our analysis findings matched other CI management interventions in that "people with chronic conditions have similar concerns and problems"(2-4). The intervention is titled *Baa nnilah*, which translates to advice or instructions for life that are received from others, often in a story form. The method for *Baa nnilah* is centered on Apsalooke cultural strengths. The content of *Baa nnilah* is based on our conceptual framework of influencers of CI management gleaned from the interview data. The measured outcomes flow directly from the conceptual framework and intervention content. *Baa nnilah* is a group intervention comprised of 10 groups of 11 tribal members: a trained facilitator, who is considered a successful manager of his/her CI, and 10 mentees, who are not managing their illness well. Each 11-member group will meet 7 times covering content and using methods outlined in our intervention manual that include a mini-discussion (lecture), talking circle and skill-building activity. The mentees will be partnered into supportive pairs who will connect a minimum of once per week outside of group meetings. Topics include those found in both our interview data and existing evidence-based self-management programs (e.g., developing a positive relationship with a healthcare provider) and Apsalooke-specific topics

from our interview data (e.g., coping with historical and current grief and loss). Consistent with the stages of behavioral therapy research(5) and using a CBPR approach, we will pursue the following Specific Aims:

Aim 1: Refine and strengthen the community-based, culturally appropriate *Baa nnilah* intervention and study protocol.

Involved will be the CAB, the Apsáalooke-based and MSU-based research team, and four potential *Aakbaabaaniilea* (facilitators). This aim will be accomplished in Year 1 and will result in a finalized training and intervention manual that will be utilized to train *Aakbaabaaniilea* and deliver the intervention.

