First of all, I would like to welcome each one of you and thank you for participating in our Báa nnilah program. Your being here shows the commitment to your health and our community. This program grew from the desires and interests of the Crow community to encourage and support people with ongoing health conditions to take good care of ourselves and in turn to support each other. We would like to ask one of the elders to provide an opening prayer to bless the gathering and the meal.

While people are eating, have them introduce each other and where they are from and one thing they are looking forward to receiving from the program. Provide the handout with the topics and dates of the 7 gatherings.

Here is a handout that shows the topics and dates for our 7 gatherings. We encourage you to come on time, stay until the end of each gathering, and to attend each of the 7 gatherings. The gatherings will be about 3 hours long. The success of Ba nnilah in improving our health and the health of our communities comes from each of us dedicating ourselves to working together and supporting each other.

- Gain knowledge and tools for healthy living and self-care to improve your quality of life.
- Learn from mentors and other program members.
- Share and apply Crow cultural strengths to address ongoing health concerns.
- Learn about nutrition and physical and emotional health tools and exercises through hands-on activities.
- Gain support and help from program staff and other participants to apply what is learned to your self-care.

Today we will complete a survey using computer tablets and we will do 3 exercises. The purpose of the survey and exercises is to help us learn how the program is progressing and what we can do to make it better. We will be reading the questions on the survey out loud and you will see the questions on the computer screen. You will respond to the questions by touching the screen. If you have a question, please raise your hand and someone will come to help you.

We thank you very much for sharing with us today. We hope you will share your true feelings, for there are no right or wrong answers to these questions. The information you share with Messengers for Health will be kept confidential and your name will not be on this survey. We have arranged the computer tablets so that no one will see your responses.

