- Since starting with the Báa nnilah program, what other support in addition to being in the program has made a difference for your health?
- In your observation, what changes have you noticed in the community as a result of this program?
- What do you see for yourself for the future?
 - What information/tips/techniques from the program will you use in the future?

- What ideas do you have for the future of the Ba nnilah program in the Crow community?

Aho. Thank you for your time today. You are helping us to make the Ba nnilah program most effective.

Facilitator measures of fidelity

1. Recruitment: Mentor will have a “Participant Notebook” where they keep track of names and contact information of community members they recruited, location of recruitment, and date of recruitment. We will also gather information on emergency contacts for each participant. We will use this notebook to track recruitment efforts. Note: The Participant Notebook will not be linked to the outcome data in order to protect confidentiality of participant information.
2. Entry into study: The Participant Notebook will also have information on the date the mentor consented the participant and the date they held a meeting with the participant to hear their health story.
3. Retention:
 - a. Each gathering will include a mentor check list of participant attendance, which the mentor will transfer into the Participant Notebook, which will be changed to number of gatherings attended by each participant in the database.
 - b. For gatherings missed by participants, the mentor will indicate if the participant provided a reason for missing the gathering
 - c. Participants who drop out of the study will be contacted by project staff (not the mentor who is leading their gatherings) and asked for their reasons for drop out.
4. Dose: Each gathering will include a mentor check list of which components of the gathering they facilitated and the length of the gathering in minutes. An example is included in the materials. The evaluation will consist of the number of manual-based intervention components delivered divided by the total number intended. The checklist also includes three questions:
 - a. How comfortable were you in leading this gathering?
Not at all comfortable to Very comfortable on a scale of 1-10
 - b. How confident were you in leading this gathering?
Not at all confident to Very confident on a scale of 1-10
 - c. Please share any comments you have about leading this gathering.

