Mentor Gathering Check List

Please complete this check list after the gathering has taken place. Please check the box to the right to show which activities you were able to complete during the gathering and answer the questions below. Return the completed check list to [name] or [name]. Thank you!

Mentor name: _____

Date of gathering: _____

Length of gathering: _____ minutes

Gathering 1: Beginning the Bábí nnilah Journey Outline

[figure not shown]
Welcoming, prayer, meal	
Story	
Mentor provides information: introduction/purpose of gathering	
Supportive partnerships activity	
Closing	
How comfortable were you in leading this gathering? Circle one number: Not at all comfortable 1 2 3 4 5 6 7 8 9 10 Very comfortable	
How confident were you in leading this gathering? Circle one number: Not at all confident 1 2 3 4 5 6 7 8 9 10 Very confident	
Please share any comments you have about leading this gathering.	

Join us!

[name], [name] and mentors who have ongoing health concerns (see back) will lead the Baa nnilah program. Messengers for Health is collaborating with all tribal entities, MSU - Bozeman and Big Horn Valley Health Center in Hardin.

Baa nnilah Program Gatherings will begin in 2017

Messengers for Health is expanding our programming to serve both men and women living with chronic illness and recurring health concerns including but not limited to arthritis, cancer, diabetes and heart disease.

Our Baa nnilah program was inspired from personal stories that community members shared with [name] about what helps and what makes it harder for them to manage their ongoing health concerns.

Crow community members who have been living with chronic health concerns and are doing well with their self-care, known as mentors, will in turn encourage others who are facing similar medical challenges. Baa nnilah mentors provide real-life experience, knowledge and cultural strength for our Crow brothers and sisters with on-going health concerns that may not be available in most medical services.

Messengers for Health will work to keep the program going long-term to help inspire a healthier Crow People.

Baa nnilah Program at a Glance

This program is free for any Crow men and women who are living with on-going health concerns and consists of a total of 7 gatherings. Participants will attend all 7 gatherings which include a free meal. Family members are welcomed to be involved and attend the gatherings.

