Weather					
Lack of transportation					
My personal health					
Deaths in the community					
Death in the family					
Personal or family crisis					
Community events					
Work schedule					
Not being informed of gathering times and locations					
Changing schedule of gatherings					
Location of gatherings					
Family member care					
Atmosphere and feeling of gatherings					
-Please explain any gathering issues:					
Other (please explain):					

2. Participants of intervention: subgroup – no changes at this time

3. Intervention facilitators. We are adding a data collection element.

There are 10 intervention facilitators who are Crow community members. They are each leading 7 gatherings/meetings in the community. We are taking a random sample of one of the 10 facilitators for each of the 7 gatherings to complete an additional fidelity evaluation. The data will be gathered by co-PI [name], a member of the Crow Nation. The evaluation instrument is below.

In addition, for process evaluation and fidelity tracking, we are keeping field notes of texts and phone call communications with the intervention facilitators. This information will provide context and a deeper understanding of the delivery of the intervention. An example of this information is when a gathering is postponed due to weather or because participants are out of town at a basketball tournament.

6. Have these requested changes been initiated?

- No – for #1, participants of intervention
- Yes – for #3, intervention facilitators

7. How will the proposed modification(s) affect study participants?

Note: Federal regulations require IRB approval prior to changing a research procedure or deviating from IRB approved documents unless it is in the best interest of or for the safety of study participants.

The only affect is that the survey (#1 above) will take approximately 5 minutes longer for participants.

		Not Completed	Partially Completed	Fully Completed	Did the Mentor add new components not in the original protocol?
Welcoming, prayer, meal	30 min				
Story	10 min				
Mentor provides information: introduction/purpose of gathering	30 min				
Sharing circle	50 min				
Supportive partnerships activity	50 min				
Closing	10 min				
Mentor Responsibility (Communication with participants, bringing all necessary materials, being on-time, etc.)					
Mentor Interactional Style (Ex. Speaking Crow, facilitation style, food choices, humor, empathy, etc.)					
Comments:					

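### The example Gathering 1 mentor checklist has no row for the sharing circle, so for that gathering the dose ratio cannot register whether the circle took place

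*Protocol*

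**What the plan says.** Item 4 (Dose) of the Protocol's Facilitator measures of fidelity names the data source: "Each gathering will include a mentor check list of which components of the gathering they facilitated and the length of the gathering in minutes". It adds "An example is included in the materials" and then gives the score: "The evaluation will consist of the number of manual-based intervention components delivered divided by the total number intended".

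The example follows under Mentor Gathering Check List and is labelled as Gathering 1. The mentor is told: "Please check the box to the right to show which activities you were able to complete during the gathering". Five activities are listed: the welcome with prayer and meal, a story, the mentor's information on the gathering's purpose, the supportive partnerships activity, and the closing.

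The later amendment that changes the data collection months also adds, under its item 3 on facilitators, an observer form. One randomly chosen facilitator out of 10 is to be observed at each of the 7 gatherings. The form lists the same five activities with planned minutes and one more, "Sharing circle", at 50 minutes. It shows no gathering number.

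Protocol section VII.A describes the group meetings as "using methods outlined in our intervention manual that include a mini-discussion (lecture), talking circle and skill-building activity". The Data Gathering Meeting script tells participants: "The gatherings will be about 3 hours long".

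**The concern.** A ratio of components delivered to components intended is only as good as the list on which delivery is recorded. If a component has no box, the mentor cannot record having delivered it, and nobody reading the form can see that it was left out. The component missing here is not minor: it has one of the two longest time slots on the observer form, and a circle of this kind is one of the three methods that section VII.A names for the programme.

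Aim 2 includes an evaluation of fidelity, and the Protocol says that fidelity is tracked to support the reliability and validity of the intervention. Readers will use the dose figure to judge how fully the programme was delivered. For the gathering concerned, the figure would be silent on a named method.

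**Working it through.** The documents give no fidelity score, no threshold and no count of intended components, so there is no stated figure to reproduce. The check compares the two lists and then works through the ratio.

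**Step 1: compare the lists.**

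| Activity | Mentor checklist, Gathering 1 | Observer form (minutes) |
|---|---|---|
| Welcome, prayer and meal | row | 30 |
| Story | row | 10 |
| Mentor's information | row | 30 |
| Sharing circle | no row | 50 |
| Supportive partnerships activity | row | 50 |
| Closing | row | 10 |

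The sharing circle is the only timed activity on the observer form that the mentor checklist lacks.

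**Step 2: check the times against the planned length.** 30 + 10 + 30 + 50 + 50 + 10 = 180 minutes, which agrees with the script's figure of about 3 hours. Without the circle the total is 180 − 50 = 130 minutes. The circle takes 50/180 = 27.8% of the session. This supports reading the circle as part of the planned gathering.

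**Step 3: work out the ratio (delivered / intended) with the five-row form as the only record of delivery.** Assume that the mentor delivers everything else.

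| Denominator | Circle skipped | Circle delivered |
|---|---|---|
| Five checklist rows | 5/5 = 100% | 5/5 = 100% |
| Six intended components | 5/6 = 83.3% | 5/6 = 83.3% |

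The two columns agree in each line. Whichever denominator was meant, the ratio does not separate a delivered circle from a skipped one. With a sixth row the scores would differ: 5/6 = 83.3% if skipped and 6/6 = 100% if delivered.

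**Step 4: see how far this reaches.** Gathering 1 accounts for 10 of the 10 × 7 = 70 gatherings in one round, or 14%. The observer sees 1 of the 10 Gathering 1 sessions in a round, so 9 of 10 rest on the mentor form alone. If a single set of seven observations serves both rounds, it is 1 of 20.

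The effect on a mentor's score over the whole programme depends on checklists that are not shown. As an illustration, assume six components at every gathering and complete forms for the other six gatherings. Seven gatherings then have 42 components, of which the forms can record 5 + 36 = 41. The programme score is 41/41 = 100% on checklist rows or 41/42 = 97.6% on intended components, again the same whether or not the circle took place at Gathering 1.

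**The case against.** **The score need not be 100%.** A reader might infer that a mentor who skips the circle always scores 100%. The rule does not say so. It divides by the number intended, in terms of the manual, and the documents never count that number. If it is six, the score is 83%. This stands. But a mentor who delivers the circle then also gets 83%, so the blindness remains.

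**The checklist is an early example.** It was filed while section VII.B says the mentor manual was still being finalised, and the observer form came later. The circle could have been added, or the checklist updated, in between. This cannot be excluded. However, section VII.A of the same application already names a talking circle, the 180 minutes fit only with the circle included, and no amendment in the available text revises the checklist.

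**The match between the forms is inferred.** The observer form shows no gathering number, section VII.A says talking circle where the form says sharing circle, and it does not say that every method is used at every gathering. These are fair limits. The other five rows agree closely enough, including the partnerships activity, to make Gathering 1 the natural match.

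**A row may have been lost.** A figure that did not survive text extraction sits just above the checklist table. The PDF should be checked, although the absent row would fall between two rows that did survive.

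**Other records might reveal a skipped circle.** The checklist records the gathering's length and invites comments, the amendment adds field notes, and mentors and investigators confer weekly. A session of about 130 minutes could prompt a question. None of these enters the ratio, and length alone does not show which activity was dropped.

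**Wider consequences.** A reader might infer that the same gap affects all seven gatherings, or that 90% of sessions are scored on a defective form because the observer sees 7 of 70. The documents show only the Gathering 1 form, so neither follows. A reader might also infer that the effectiveness result is at risk. The SAP model uses the number of gatherings attended and not the dose ratio, so no planned test is touched.

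**Conclusion.** The point holds for Gathering 1. As the forms stand, the dose ratio for that gathering carries no information on a component planned at 50 of 180 minutes: it is 100% or 83% depending on an unstated denominator, and the same either way for mentors who did and did not hold the circle.

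This rests on three assumptions: that the observer form corresponds to Gathering 1, that the sharing circle is a manual component of that gathering, and that the example checklist is the form that was used. The first two are well supported by the matching rows, the 180-minute total and section VII.A. The third cannot be confirmed from the documents.

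The consequence is confined to the fidelity evaluation. It is a small, easily corrected gap in a process measure.

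**What to change.** - Add a sharing circle row to the Gathering 1 mentor checklist.
- Check the other six gatherings' checklists against the final manual and the observer form. State the resulting component list and count for each gathering, and use it as the denominator of the dose ratio.
- For data already collected on the five-row form, report that the Gathering 1 ratio does not capture the sharing circle. If an updated checklist was in fact used, say so and show it.

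The new row costs one line on a form and no added staff time worth counting. Aligning the seven checklists is a one-off desk check against the manual. The last step is a sentence in the report.

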**Montana State University
Institutional Review Board
Request for Minor Modifications/Amendments**

Instructions: E-mail completed form and all revised and/or new study documents to:
[contact]

Note: The project's IRB-approved Research Protocol must be kept current and followed throughout the life of the project with yearly renewals. Protocols approved in the Exempt category do not require yearly renewals. All study documents are subject to review.

1. IRB approval number: SH082017

2. Project Title: The Ba nnilah project

3. Principal Investigator: [name]

Contact information (phone/e-mail): [name]; [contact]

4. Requesting modification/amendment to:

- Research protocol
- Consent form
- Recruitment materials
- Survey instrument, interview questions
- Research personnel
- Other, please explain:

5. Describe the modification being requested:

Note: with each requested change, provide a detailed description of where within the study documents (e.g. Research protocol, survey instrument, etc.) the changes are reflected (e.g., section, question #, etc.)

In response to a recent National Institutes of Health policy update regarding Certificates of Confidentiality, we have prepared an Addendum to our Informed Consent for our IRB approval for "The Ba nnilah project," approval SH082017. The policy update provides all NIH funded human subjects research with a Certificate of Confidentiality, which provides additional privacy protections for data collected during the *Baa nnilah* project. More information regarding the policy update is available within NOT-OD-17-109 and at <https://humansubjects.nih.gov/coc/index>.

We are seeking your approval to add the attached document to our informed consent form. We would like to provide the information to participants who were already consented and attended the data collection meetings (10 people) and add it to our form for those who have not received consent or who have not attended the data collection meetings (about 190 people).

6. Have these requested changes been initiated?

No
 Yes

We had a data collection meeting last night – October 24, 2017 and we handed out the additional information below to 5 participants.

7. How will the proposed modification(s) affect study participants?

Note: Federal regulations require IRB approval prior to changing a research procedure or deviating from IRB approved documents unless it is in the best interest of or for the safety of study participants.

We would like to make amendments to our IRB application that was approved last fall. In the application, we have three different groups of people from whom data will be gathered.

1. Participants of intervention: all participants
2. Participants of intervention: subgroup
3. Intervention facilitators

1. Participants of intervention: all participants. There are two changes – one to the timeline and one to add a data collection element.

For this group, the actual timeline for group data collection is different from what was proposed in the application. The application has data gathering events occurring in March 2018, August 2018, and December 2018 for the intervention participants. The actual months will be April/May 2018, October/November 2018, and April 2019.

We are proposing to add a data collection element for the intervention participants. All participants attend 7 gatherings as a part of the intervention. The intervention is led by facilitators who are members of the Crow community. Project staff members will send postcard reminders the week before each gathering and text or phone call reminders to participants on the day of each of the 7 gatherings. Project staff will save participant phone numbers only by participant ID number versus by name. Any responses to the text or phone reminders will be archived, again only by participant ID. Additionally, we would like to add questions to the post-intervention survey to ascertain how well each of the retention strategies helped participants to keep attending each of the gatherings (to improve and track participant retention). The questions are below and will be answered on computer tablets with the already approved surveys.

Please check how much each of the following helped you to keep coming to the gatherings

	Not at All	A Little Bit	Somewhat	Quite a Bit	Very Much
Newsletter					
Gifts received at gatherings					
Gas cards received at gatherings					
My supportive partner					
Information I learned at the gatherings					
My personal motivation					
Collecting my feathers (goals)					
Healthy meals at gatherings					
My relationship with my mentor					
My bonding with other participants					
Location of gatherings					
Postcard reminders					
Phone texts/calls from MSU team members					
Phone texts/calls from my mentor					
Other (please explain):					

Please check how much each of the following prevented you from attending the gatherings

	Not at All	A Little Bit	Somewhat	Quite a Bit	Very Much
Weather					
Lack of transportation					
My personal health					
Deaths in the community					
Death in the family					
Personal or family crisis					
Community events					
Work schedule					
Not being informed of gathering times and locations					
Changing schedule of gatherings					
Location of gatherings					
Family member care					
Atmosphere and feeling of gatherings					
-Please explain any gathering issues:					
Other (please explain):					

2. Participants of intervention: subgroup – no changes at this time

3. Intervention facilitators. We are adding a data collection element.

There are 10 intervention facilitators who are Crow community members. They are each leading 7 gatherings/meetings in the community. We are taking a random sample of one of the 10 facilitators for each of the 7 gatherings to complete an additional fidelity evaluation. The data will be gathered by co-PI [name], a member of the Crow Nation. The evaluation instrument is below.

In addition, for process evaluation and fidelity tracking, we are keeping field notes of texts and phone call communications with the intervention facilitators. This information will provide context and a deeper understanding of the delivery of the intervention. An example of this information is when a gathering is postponed due to weather or because participants are out of town at a basketball tournament.

6. Have these requested changes been initiated?

- No – for #1, participants of intervention
- Yes – for #3, intervention facilitators

7. How will the proposed modification(s) affect study participants?

Note: Federal regulations require IRB approval prior to changing a research procedure or deviating from IRB approved documents unless it is in the best interest of or for the safety of study participants.

The only affect is that the survey (#1 above) will take approximately 5 minutes longer for participants.

		Not Completed	Partially Completed	Fully Completed	Did the Mentor add new components not in the original protocol?
Welcoming, prayer, meal	30 min				
Story	10 min				
Mentor provides information: introduction/purpose of gathering	30 min				
Sharing circle	50 min				
Supportive partnerships activity	50 min				
Closing	10 min				
Mentor Responsibility (Communication with participants, bringing all necessary materials, being on-time, etc.)					
Mentor Interactional Style (Ex. Speaking Crow, facilitation style, food choices, humor, empathy, etc.)					
Comments:					
Participant & Environmental Factors (Ex. Health condition, weather, deaths, presence of people not in the program, etc.)					
Comments					

**Montana State University
Institutional Review Board
Request for Minor Modifications/Amendments**

Instructions: E-mail completed form and all revised and/or new study documents to:
[contact]

Note: The project's IRB-approved Research Protocol must be kept current and followed throughout the life of the project with yearly renewals. Protocols approved in the Exempt category do not require yearly renewals. All study documents are subject to review.

- 1. IRB approval number:** SH082017
- 2. Project Title:** The baa nnilah project
- 3. Principal Investigator: [name]**
Contact information (phone/e-mail): [name]/[contact]
- 4. Requesting modification/amendment to:**
 Research protocol
 Consent form
 Recruitment materials
 Survey instrument, interview questions
 Research personnel
 Other, please explain:

- 5. Describe the modification being requested:**
Note: with each requested change, provide a detailed description of where within the study documents (e.g. Research protocol, survey instrument, etc.) **the changes are reflected** (e.g., section, question #, etc.)

We would like to make amendments to our IRB application that was approved last fall. In the application, we have three different groups of people from whom data will be gathered.

1. Participants of intervention: all participants
2. Participants of intervention: subgroup
3. Intervention facilitators

1. Participants of intervention: all participants. There are three additions we would like to make to our data collection.

First addition: To gather accurate data for adverse reporting, we would like to add these questions to the computer tablets:

- ❖ Since you last took this survey have you been in a hospital overnight because of your health?

Yes/no

Since you last took this survey have you been to the emergency room because of your health?

Yes/no

Second addition: The first question below was on our original protocol to gathering information on contamination from the wait-list control group. We would like to add the second and third question.

1. The Messengers for Health Baa nnilah program consists of 7 gatherings in the local Crow communities and Hardin that are led by a community member mentor. Have you taken action for your health because of something you have heard or learned from a friend or family member who has attended the gatherings?

Yes (if they choose this, go to the next two)

No

2. To what extent have you taken action from what you learned? Please choose the number that best describes your action taken:

(not at all) 0 1 2 3 4 5 6 7 8 9 10 (A lot)

3. Please share what actions you have taken or changes you have made in your life because of what you heard or learned from a friend or family member who has attended the gatherings (open ended-question):

Third addition: We are proposing to add a data collection element for the intervention participants. All participants attend 7 gatherings as a part of the intervention. The intervention is led by facilitators who are members of the Crow community. During the intervention, participants receive incentives related to health. We want to know if these incentives are being used. At the data gathering meeting, we will put the incentive on a table with a sheet of paper asking: "How often did you use this?" Participants who attended the intervention will put a check mark by the response that represents their behavior. There will also be space where they can write comments. Below is a table that shows the incentives and scale.

	Not at all	Rarely	Sometimes	Often	All the time
Medication tracking sheet					
Preparing for your doctor visit					
Business card doctor visit					
Exercise bands					
Walking a good path					
Ground, breathe, settle bracelet					
Living a healthy life book					
Wrist activity tracker (fit bit)					
Journal					

2. Participants of intervention: subgroup – no changes at this time

3. Intervention facilitators. – no changes at this time

6. Have these requested changes been initiated?

- No
- Yes

7. How will the proposed modification(s) affect study participants?

Note: Federal regulations require IRB approval prior to changing a research procedure or deviating from IRB approved documents unless it is in the best interest of or for the safety of study participants.

The only affect is that the data collection time will take approximately 5 minutes longer for participants.

**Montana State University
Institutional Review Board
Request for Minor Modifications/Amendments**

Instructions: E-mail completed form and all revised and/or new study documents to:
[contact]

Note: The project's IRB-approved Research Protocol must be kept current and followed throughout the life of the project with yearly renewals. Protocols approved in the Exempt category do not require yearly renewals. All study documents are subject to review.

- 1. IRB approval number:** SH082017
- 2. Project Title:** Improving chronic illness management with the Apsaalooke Nation: The báa nnilah project
- 3. Principal Investigator:** [name]
Contact information (phone/e-mail): [name]/[contact]
- 4. Requesting modification/amendment to:**

Research protocol
 Consent form
 Recruitment materials
 Survey instrument, interview questions
 Research personnel
 Other, please explain:

- 5. Describe the modification being requested:**

Note: with each requested change, provide a detailed description of where within the study documents (e.g. Research protocol, survey instrument, etc.) the changes are reflected (e.g., section, question #, etc.)

We would like to make amendments to our IRB application that was approved August 2017. In the application, we have three different groups of people from whom data will be gathered.

1. Participants of intervention: all participants
2. Participants of intervention: subgroup
3. Intervention facilitators

We would like to make amendments to #2 and #3.

2. Participants of intervention: subgroup. This is a random sample of #1. The participants will complete an interview with project staff. The interview protocol was approved in August 2017. We would like to make minor modifications to some of the questions. The protocol showing track changes is below.

3. Intervention facilitators. We would like to add an interview to be conducted by project staff with the intervention facilitators. The interview protocol is below.

6. Have these requested changes been initiated?

No
Yes

7. How will the proposed modification(s) affect study participants?

Note: Federal regulations require IRB approval prior to changing a research procedure or deviating from IRB approved documents unless it is in the best interest of or for the safety of study participants.

This will not affect study participants except the minor changes to the interview protocol for a subsample of participants (#2) and an additional interview for #3, which will take approximately 1 hour of their time.

2. Participants of intervention: subgroup

Báa nnilah program qualitative interview questions

Hello. I am [name]. Thank you for agreeing to talk about your experiences with the Báa nnilah program. We plan to use the information shared in the interviews to improve the program for the future. We hope you will share with us your true feelings, for there are no right or wrong answers to these questions. We will be tape-recording our conversation so that we make sure to receive everything that you have to share. Participation in this interview is voluntary and you can choose to either share your name or have the information you share be anonymous, meaning that your name will not appear anywhere. You can stop the interview at anytime or not answer any question. The interview will take about one hour of your time and you will be paid a \$30 gift card to thank you for your help. Let's begin.

- How did participating in the Báa nnilah program influence your life?
 - Probe if needed: Can you tell me more about that?
 - Probe if needed: Can you give me an example?
- How did your Báa nnilah program mentor influence your life?
 - What did you learn from your mentor?
 - How did the mentor's teaching style influence your learning?
- What have you shared about the program with family members, community members and others?
 - Could you give me some of examples of how you have shared about this program?
- What have you changed about your self-care after participating in the Báa nnilah program?
 - What information/tips/techniques from the Báa nnilah program did you apply or are you applying to your own life?
- In what ways, if at all, has attending the Báa nnilah program changed how you share about your health with others?
- What has changed in your relationships with your family and friends since being in the Báa nnilah program?
- Have you seen your doctor since participating in the program?
 - If no, go to "How has this program..."
 - If yes, continue to the next question.
- What has changed in your relationship with your doctor since being in the Báa nnilah program?
 - How has the communication between you and your doctor changed?
 - How has your doctor's attitude changed since being in Báa nnilah?
 - Probe if they don't mention these: how about their concern and thoroughness?
 - How has the doctor's behavior and treatment toward you changed?
- How has this program influenced your feelings of hope toward your health?

Give participant the list of gathering topics for the next set of questions.

